10.1. Response Criteria

Investigators will use RECIST 1.1 and irRECIST to assess tumor response for subjects treated with CC-122 in combination with Nivolumab (see Table 4).

Table 4: Time Point Overall Tumor Response Definitions by RECIST 1.1 and irRECIST

Overall Response RECIST 1.1	RECIST 1.1 ^[1]	Overall Response irRECIST	irRECIST ^[2]
CR	Disappearance of all target lesions, disappearance of all non-target lesions and normalisation of tumor marker level. All lymph nodes must be non-pathological in size (<10mm short axis).	irCR	Complete disappearance of all measurable and non-measurable lesions. Lymph nodes must decrease to < 10 mm in short axis. Confirmation of response is not mandatory.
PR	At least a 30% decrease in the sum of diameters of target lesions, taking as reference the baseline sum diameters, no unequivocal progression of non-target lesions and no new lesion(s), but the criteria for CR are not met	irPR	Decrease of $\geq 30\%$ in TMTB relative to baseline, non-target lesions are irNN, and no unequivocal progression of new non-measurable lesions.
SD	Neither sufficient shrinkage in the sum of diameters of target lesions to qualify for PR nor sufficient increase to qualify for PD, taking as reference the smallest sum diameters while on study, no unequivocal progression of non-target lesions and no new lesion(s).	irSD	Failure to meet criteria for irCR or irPR in the absence of irPD.
PD	At least a 20% increase in the sum of diameters of target lesions from nadir. In addition, the sum must also demonstrate an absolute increase of at least 5 mm, or unequivocal progression of non-target lesions, or appearance of new lesion(s).	irPD	At least 20% increase and minimum 5 mm absolute increase in TMTB compared to nadir, or irPD for non-target or new non-measurable lesions. Confirmation of progression is recommended minimum 4 weeks after the first irPD assessment.

Abbreviations: CR = Complete Response; PR = Partial Response; SD = Stable Disease; PD = Progressive Disease; ir=immune-related; irNN = irNon-CR/Non-PD, TMTB = total measured tumor burden,

^[1] RECIST 1.1 overall response is based on the sum of diameters of the target lesions.

^[2] irRECIST overall response is based on TMTB for target and new measurable lesions.

Table 5: RECIST 1.1 Best Overall Response When Confirmation of CR and PR is Required

Overall Response First Time Point	Overall Response Subsequent Time Point	Best Overall Response
CR	CR	CR
CR	PR	SD, PD or PR ^[1]

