CR	SD	SD provided minimum criteria for SD duration met, otherwise, PD
CR	PD	SD provided minimum criteria for SD duration met, otherwise, PD
CR	NE	SD provided minimum criteria for SD duration met, otherwise NE
PR	CR	PR
PR	PR	PR
PR	SD	SD
PR	PD	SD provided minimum criteria for SD duration met, otherwise, PD
PR	NE	SD provided minimum criteria for SD duration met, otherwise NE
NE	NE	NE

Abbreviations: CR = complete response, PR = partial response, SD = stable disease, PD = progressive disease, NE = non evaluable.

[1] If a CR is truly met at first time point, then any disease seen at a subsequent time point, even disease meeting PR criteria relative to baseline, makes the disease PD at that point (since disease must have reappeared after CR). Best response would depend on whether minimum duration for SD was met. However, sometimes 'CR' may be claimed when subsequent scans suggest small lesions were likely still present and in fact the subject had PR, not CR at the first time point. Under these circumstances, the original CR should be changed to PR and the best response is PR.

Note: All responses after first PD will not be considered as a response.

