10.2. Best Overall Response (BOR)

Confirmed and unconfirmed BOR (or irBOR) will be summarized using frequency tabulation for the Safety Population and EE Population, separately.

Confirmed BOR will only be used to summarize ORR by RECIST1.1, with unconfirmed BOR used in the derivation of ORR, DCR, sustained DCR, DoR, duration of SD, PFS and TTP.

Unconfirmed BOR will be used for graphs.

Figures of tumor assessment will be provided, which include:

- Waterfall plots: Each subject's best percent change as defined below will be represented by a bar, with a pattern specific to the dose cohort to which they were initially assigned to (in the dose escalation part) and designated subgroup (in dose expansion part), and with their overall relative dose intensity annotated below/above each bar. For each study phase, a separate graph on the next page will be produced.
 - For RECIST 1.1, a waterfall plot of best percentage change from baseline in the sum of diameters (longest for non-nodal lesions, short axis for nodal lesions) of target lesions for all subjects with non-missing target lesion.
 - For irRECIST, waterfall plot for best percent change from baseline in TMTB, for all subjects with non-missing TMTB.
- Spider plots: Each subject's percent change from baseline as defined below, will be represented by lines with a colour specific to the dose cohort to which they were initially assigned to (in the dose escalation part) and designated subgroup (in dose expansion part). For each phase, a separate graph on the next page will be produced.
 - For RECIST 1.1, a spider plot of percent change from baseline in target lesions by time from first dose.
 - For irRECIST, a spider plot of percent change from baseline in TMTB by time from first dose

Unconfirmed BOR - RECIST 1.1

Unconfirmed BOR is the best of overall response across all time points evaluated by investigator using RECIST 1.1 criteria as defined in [Table 4](#). The order in which responses are rated are CR, PR, SD, Progressive Disease (PD), not evaluable (NE). BOR is derived from post-baseline responses up until the date of progression or data cut-off date if progression has not occurred prior to the cut-off date. For example, if a subject has overall responses of PR, SD and PD, the unconfirmed BOR would be PR.

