Duration of SD must meet minimum duration for at least 6 weeks if the BOR is SD. If the minimum time for a best response of SD is not met, the subject's best response depends on the subsequent assessments.

For example:

- A subject who has SD at the first assessment, PD at the second but does not meet minimum duration for SD, will have a best response of PD. PD assessment does not

required to be confirmed. A subject who has SD at the first assessment and is then lost to follow-up would be considered not evaluable.

Confirmed BOR – RECIST 1.1

Confirmed BOR is derived using Table 5 to confirm the best response. Confirmation of response requires repeat assessment of response (CR or PR) at the next scheduled scan more than 4 weeks following the first assessment meeting response criteria. If best overall response is SD, it must meet the minimum duration of 6 weeks. If the minimum time for a best response of SD is not met, the subject's best response depends on the subsequent assessments.

irBOR – irRECIST

In irRECIST, the determination of the adaptation of the immune-related unconfirmed best overall response (irBOR) is the single best immune-related response of overall response across all time points (post-baseline) evaluated by investigator using irRECIST criteria defined in Table 4. The order in which responses are rated are irCR, irPR, irSD, irPD, irNE. For example if a subject has overall responses of irPR, irSD and irCR, the unconfirmed irBOR would be irCR. The same minimum duration of SD required in RECIST 1.1 must be met if the best overall response is irSD.

Objective Response Rate (ORR) and Disease Control Rate (DCR)

Unconfirmed ORR, confirmed ORR, DCR and sustained DCR will be derived separately for investigator RECIST 1.1 and irRECIST assessment [REDACTED]

Table 6: ORR and DCR Derivation rules

Endpoint	Confirmed	Criteria	Derivation
ORR	Yes	RECIST 1.1	Confirmed BOR of CR or PR
	No	RECIST 1.1	Unconfirmed BOR of CR or PR
	No	irRECIST	Unconfirmed irBOR of CR or PR
DCR	No	RECIST 1.1	Unconfirmed BOR of CR, PR or SD
	No	irRECIST	Unconfirmed irBOR of CR, PR or SD
Sustained DCR	No	RECIST 1.1	Unconfirmed BOR of CR, PR or SD (duration of SD \geq 16 weeks)
	No	irRECIST	Unconfirmed irBOR of CR, PR or SD (duration of SD \geq 16 weeks)

Abbreviations: BOR = best overall response; CR = complete response, SD = stable disease, PR = partial response, ir = immune related

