10.3. Duration of Response (DoR) and duration of SD

DoR and duration of SD are derived for RECIST 1.1 and irRECIST separately and are defined as per the rules in Table 7.

Table 7: DoR and Duration of SD Derivation Rules

Endpoint	Derivation	Common Censoring Rules
DoR	
For subjects with an unconfirmed BOR of PR or CR:
 
DoR is measured from the date the criterion is first met for CR/PR (whichever is first recorded) until the first date when PD is documented or death occurred.
	
If the subject is still alive and did not experience PD at the date of cutoff, DoR and duration of SD will be censored at the date of last adequate¹ post-baseline tumor assessment prior to the cutoff date.
 
If a subject progresses or dies after an extended lost-to-follow up time (two or more missed assessments), DoR and duration of SD will be censored on the date of last adequate tumor assessment.

Duration of SD	
For subjects with an unconfirmed BOR of SD:
 
Duration of SD is measured from the first dose date (i.e. the first dose of CC-122 or Nivolumab whichever occurred first) until the first date when PD is documented or death occurred.
	

Abbreviations: BOR = best overall response; CR = complete response, SD = stable disease, PD = progressive disease, PR = partial response.

¹ Adequate tumor assessment is defined as the latest tumor assessment which is not missing or recorded as “not done” or “not all evaluable”.

The Kaplan-Meier estimate of median DoR and SD for both RECIST 1.1 and irRECIST along with a 2-sided 95% CI ([REDACTED]) will be provided by using Safety and EE Populations. The Kaplan-Meier estimate will only be provided for the phase and dose cohort/subgroup where the following conditions are met:

- DoR (RECIST 1.1): at least 3 subjects have unconfirmed DCR;
- DoR (irRECIST): at least 3 subjects have unconfirmed irDCR;
- Duration of SD (RECIST 1.1): at least 3 subjects with BOR of SD;

- Duration of SD (irRECIST): at least 3 subjects with irBOR of SD.

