10.5. Progression-Free Survival (PFS) and Time to Progression (TTP)

10.5.1. Progression-Free Survival (PFS)

PFS is defined as the time from the first dose date until tumor progression or death, whichever occurs first.

Based on Food and Drug Administration (FDA) Guidance () a subject who has neither progressed nor died or who progresses or dies after an extended lost-to-follow up time (two or more missed assessments) will be censored on the date of last adequate tumor assessment. Subjects without valid baseline or post-baseline tumor assessments will be censored on their first dose date (i.e. the first dose of CC-122 or Nivolumab whichever occurred first). Censoring rules are defined in [Table 8](#).

For PFS by irRECIST, the date of progression is the first date of PD as defined under irRECIST.

Analysis of PFS will be provided for RECIST and irRECIST separately and be presented for the Safety and EE Populations. Median of PFS times will be calculated using the Kaplan-Meier method and the corresponding 95% CIs will be presented. The number of events, subjects censored, and the Kaplan-Meier estimates of PFS rates at the time points of 3 months (90 days) and 6 months (180 days), along with standard errors of rate estimates (Greenwood’s formula,) will also be provided.

Table 8: Progression and Censoring Rules for PFS Analysis

Situation	Date of Progression or Censoring	Outcome
No baseline assessment	Date of first dose of study drug	Censored
No progression	Date of last visit with adequate assessment	Censored
Treatment discontinuation for toxicity or other reason without progression	Date of last visit with adequate assessment	Censored
New anticancer treatment started with no claim of progression	Date of last visit with adequate assessment	Censored
Death before first PD assessment	Date of death	Progressed
Death between adequate assessment visits or after patient misses one assessment visit	Date of death	Progressed
Death or progression after an extended lost-to-follow up time (two or more missed assessments)	Last visit with adequate assessment	Censored

In dose expansion phase, for the Safety and EE Populations, Kaplan-Meier survival curves of PFS will be presented for RECIST 1.1 and irRECIST separately; subgroup will be presented in the same figure using different lines colour/symbol.

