10.5.2. Time to Progression (TTP)

TTP is defined as the time from the first dose date (i.e. the first dose of CC-122 or Nivolumab whichever occurred first) until tumor progression; TTP does not include death. The censoring rules for TTP are the same as described for PFS, except deaths without progression are censored at the time of the date of last adequate tumor assessment.

For TTP by RECIST 1.1, a subject who has not progressed will be censored on the date of last adequate tumor assessment. Subjects without valid baseline or post-baseline tumor assessments will be censored on their first dose dates. Any valid overall post-baseline tumor assessment (not recorded as “not done” or “not all evaluable”) are considered adequate tumor assessments in this case.

For TTP by irRECIST, the date of progression is the first date of PD as defined under irRECIST. A subject who has not progressed or who progresses or dies after an extended lost-to-follow up time (two or more missed assessments) will be censored on the date of his or her last adequate tumor assessment. Subjects without valid baseline or post-baseline tumor assessments will be censored on their first dose dates (i.e. the first dose of CC-122 or Nivolumab whichever occurred first).

Analysis of TTP will be provided for RECIST and irRECIST separately and presented for the Safety and EE Populations. Median of TTP will be calculated using the Kaplan-Meier method and the corresponding 95% CIs will be presented.

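### In the exploratory irRECIST analyses, irBOR can count a response after an irPD, while irPFS, irTTP and, read literally, irDoR end at that first irPD

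*SAP*

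**What the plan says.** **RECIST 1.1.** SAP 10.2 closes the response window at progression: "BOR is derived from post-baseline responses up until the date of progression or data cut-off date if progression has not occurred". The footnote to Table 5 in SAP 10.1, a table titled for confirmed RECIST 1.1 response, adds "Note: All responses after first PD will not be considered as a response".

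**irRECIST response.** For irBOR, SAP 10.2 uses Table 4 and a different window: irBOR "is the single best immune-related response of overall response across all time points (post-baseline) evaluated by investigator using irRECIST criteria". Table 6 builds irORR on this ("Unconfirmed irBOR of CR or PR"), and likewise irDCR and sustained irDCR, the last requiring SD of at least 16 weeks. In Table 4, irPR is judged against baseline and irPD against nadir. On irPD, Table 4 says "Confirmation of progression is recommended minimum 4 weeks after the first irPD assessment".

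**irRECIST time-to-event.** SAP 10.3 applies Table 7 to RECIST 1.1 and to irRECIST. DoR starts at the first CR or PR and duration of SD starts at first dose; both run "until the first date when PD is documented or death occurred". SAP 10.5.1 states "For PFS by irRECIST, the date of progression is the first date of PD as defined under irRECIST", and SAP 10.5.2 states "For TTP by irRECIST, the date of progression is the first date of PD as defined under irRECIST".

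**Data collection.** Protocol 6.5.4 starts irRECIST evaluation when treatment continues past RECIST 1.1 progression. Protocol 6.5.2 asks for a rescan 4 to 6 weeks after that progression, and leaves later imaging to standard of care.

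**The concern.** The RECIST 1.1 rules agree with each other: responses stop counting at progression, and progression ends the time-to-event endpoints. The irRECIST rules do not share a closing date. irBOR stays open after an irPD, while the other quantities close at the first irPD whether or not a rescan bears it out. The SAP has no rule for an irPD that comes before a response or before lasting stable disease.

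That sequence is not remote. The protocol collects irRECIST data in subjects treated past progression and rescans them to see whether the tumour has shrunk. For such a subject the irRECIST listings and summaries would show a responder who had already progressed. The duration of response would be either negative or measured to a progression date that irPFS and irTTP do not use. Two programmers could follow the SAP faithfully and produce different irDoR values.

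**Working it through.** The plan states no figure on this point, so there is none to reproduce. The check applies the SAP rules to a constructed subject.

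**Inputs**
- First dose is Day 1 (SAP 17.2.1), so Week w falls on Day 1 + 7w.
- Scans are every 8 weeks (SAP 10); the rescan is 4 to 6 weeks after progression (Protocol 6.5.2).
- Months = days / 30.4167 (SAP 17.2.1).
- Assumed timeline: irPD at Week 8 (Day 57); irPR at Week 12 (Day 85), Week 14 (Day 99) or, as an illustration of a later scan, Week 16 (Day 113); a second irPD at Week 40 (Day 281).
- Illustrative burden: baseline 100 mm, then 125 mm (+25%, irPD), then 65 mm (-35% from baseline, irPR). The Table 4 definitions allow this order.

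**Case 1: irPD, then irPR**
- irBOR is the best of irPD, irPR and irPD, which is irPR. The subject counts in irORR and irDCR.
- irPFS and irTTP are events on Day 57 (57 / 30.4167 = 1.87 months). The subject fails both the 90-day and the 180-day irPFS rate.
- For irDoR, Table 7 gives a start and an end but no explicit formula. The two readings are:

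| Response at | Literal: first irPD minus response day | Same, plus 1 day | First PD after response: 281 minus response day, plus 1 |
|---|---|---|---|
| Week 12 | 57 - 85 = -28 days | -27 | 197 days (6.48 months) |
| Week 14 | 57 - 99 = -42 days | -41 | 183 days (6.02 months) |
| Week 16 | 57 - 113 = -56 days | -55 | 169 days (5.56 months) |

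The literal reading is unusable. The other reading gives a sensible duration, but it ends on Day 281 while irPFS and irTTP for the same subject end on Day 57.

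**Case 2: irPD at Week 8, then lasting irSD**
- irBOR is irSD; the 6-week minimum is met by Week 8.
- Duration of SD ends at the first irPD, after about 8 weeks. Since 8 is below 16, the subject fails sustained irDCR however long the later irSD lasts.

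**Contrast.** Case 1 under the RECIST 1.1 rules gives BOR of PD, no DoR and a PFS event on Day 57, with no conflict. The problem is confined to irRECIST.

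**Case 1 after each repair**
- One qualifying irPD date: irBOR is irPR, irPFS and irTTP events fall on Day 281 (9.24 months), and irDoR is 197, 183 or 169 days. irORR does not change.
- irBOR cut at the first irPD: irBOR is irPD, there is no irDoR, and events stay on Day 57. irORR loses this subject.

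**The case against.** **The Table 5 footnote already bars later responses.** It sits under a table for confirmed RECIST 1.1 response, whereas irBOR is unconfirmed and refers to Table 4. If it was meant to govern irBOR, the all-time-points wording needs correcting. This objection does not stand.

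**Table 7 naturally means the first PD after the response.** This is a fair reading, and it removes the negative durations. A reader might infer that irDoR is impossible to compute; the text does not force that. What remains is that Table 7 does not say so, and that irDoR then parts company with irPFS and irTTP.

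**A progression event and a best response of irPR are separate endpoints and can both be recorded.** True. Ending duration of SD at the first irPD can also be defended as a conservative convention. The fault is the lack of a common date, not a logical impossibility in every endpoint.

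**Not every pseudo-progressor is affected.** Correct. Table 4 adds new measurable lesions to the tumour burden, so a new measurable lesion can be RECIST 1.1 PD without being irPD. Only subjects whose first progression itself meets irPD are caught.

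**irRECIST is exploratory and the trial has shrunk.** Correct. Protocol 6.5.4 says that irRECIST does not determine treatment. SAP 15 item 2 cancels the expansion phase and drops exploratory efficacy analyses that the data cannot support. SAP 10.3 also withholds Kaplan-Meier irDoR from groups with fewer than 3 subjects with irDCR. But item 2 does not name irRECIST, and SAP 10 still specifies the irRECIST listings and summaries.

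**The full irRECIST definitions are elsewhere.** Protocol 6.5.4 points to Appendix C, which is not in the text available here, so a confirmation rule there cannot be ruled out. The SAP derivations, as they stand, refer to the first irPD.

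**Conclusion.** The point holds as a minor inconsistency. For a subject whose first progression meets irPD and who later has irPR or irCR, the SAP yields an irORR responder with an irPFS and irTTP event before the response. irDoR is then either negative (-28 to -42 days at the 4 to 6 week rescan) or tied to a different PD date. For irPD at Week 8 followed by lasting irSD, irBOR and sustained irDCR point in different directions. The day counts rest on the assumed timeline; the conflict itself rests only on the order of events.

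Two stronger inferences are not supported. First, the RECIST 1.1 primary and secondary endpoints are not affected, since their response window closes at progression. Second, a reader might think that irORR is inflated by 1/6, or 17 percentage points, per such subject in a cohort of 6. Under the repair recommended below the subject is a responder before and after, so irORR moves by 0 points. A shift of that size (or 1/20, 5 points, at 20 subjects) would arise only if the sponsor chose to cut irBOR at the first irPD.

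**What to change.** Define one qualifying irPD date in SAP 10.1. Use it to close the irBOR window and to end irDoR, duration of irSD, irPFS and irTTP.

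- The first irPD qualifies if it is confirmed at an evaluable scan at least 4 weeks later.
- It also qualifies if no evaluable scan at least 4 weeks later exists. This covers death, a non-evaluable rescan, and a rescan done only before 4 weeks.
- It does not qualify if that scan shows irSD, irPR or irCR. Any later irPD is then tested in the same way.
- State in Table 7 that, for irRECIST, DoR ends at the qualifying irPD or death after the response.

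The cost is SAP wording and one derived date. The rescan is already in Protocol 6.5.2, so no new scan is needed and no treatment rule changes. The consequence to accept is later irPFS and irTTP times for these subjects.

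If the sponsor prefers to keep the first irPD as the event, irBOR must be cut at that same date. That is also consistent, but it discards responses seen after an unconfirmed irPD and lowers irORR accordingly. The SAP should state which of the two applies.

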10.3. Duration of Response (DoR) and duration of SD

DoR and duration of SD are derived for RECIST 1.1 and irRECIST separately and are defined as per the rules in Table 7.

Table 7: DoR and Duration of SD Derivation Rules

Endpoint	Derivation	Common Censoring Rules
DoR	
For subjects with an unconfirmed BOR of PR or CR:
 
DoR is measured from the date the criterion is first met for CR/PR (whichever is first recorded) until the first date when PD is documented or death occurred.
	
If the subject is still alive and did not experience PD at the date of cutoff, DoR and duration of SD will be censored at the date of last adequate¹ post-baseline tumor assessment prior to the cutoff date.
 
If a subject progresses or dies after an extended lost-to-follow up time (two or more missed assessments), DoR and duration of SD will be censored on the date of last adequate tumor assessment.

Duration of SD	
For subjects with an unconfirmed BOR of SD:
 
Duration of SD is measured from the first dose date (i.e. the first dose of CC-122 or Nivolumab whichever occurred first) until the first date when PD is documented or death occurred.
	

Abbreviations: BOR = best overall response; CR = complete response, SD = stable disease, PD = progressive disease, PR = partial response.

¹ Adequate tumor assessment is defined as the latest tumor assessment which is not missing or recorded as “not done” or “not all evaluable”.

The Kaplan-Meier estimate of median DoR and SD for both RECIST 1.1 and irRECIST along with a 2-sided 95% CI ([REDACTED]) will be provided by using Safety and EE Populations. The Kaplan-Meier estimate will only be provided for the phase and dose cohort/subgroup where the following conditions are met:

- DoR (RECIST 1.1): at least 3 subjects have unconfirmed DCR;
- DoR (irRECIST): at least 3 subjects have unconfirmed irDCR;
- Duration of SD (RECIST 1.1): at least 3 subjects with BOR of SD;

- Duration of SD (irRECIST): at least 3 subjects with irBOR of SD.

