6.4.3. Survival Follow-up

After the EOT visit, all subjects will be followed for survival status either until death, lost to follow-up, or until two years from enrollment, whichever event occurs first. This evaluation should be conducted every 3 months (± 7 days) thereafter. New anticancer therapies will also be collected at the same schedule. New anticancer therapy includes (but is not limited to) any systemic or locoregional medication, surgery, radiation, or any other therapy intended to treat the subject's cancer.

Survival follow-up may be conducted by record review (including public records) and/or telephone contact with the subject, family, or the subject's treating physician.

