8.4. Prior Therapies for This Disease

The number of prior therapies/surgeries will be summarized for prior radiation therapies, prior cancer surgeries, prior systemic anti-cancer therapies, prior hormonal anti-cancer therapies, prior stem cell transplants and prior locoregional therapy for this disease separately and overall by frequency tabulations for the Safety Population. The therapies/surgeries with the same sequence/regimen number are counted as one prior therapy/surgery. Listings of therapies for this disease will also be presented by categories (prior, concomitant, and follow-up) for the Enrolled Population. Prior therapies are the therapies that were started before the first dose of study drug. Concomitant therapies are the therapies that were started on or after the first dose of study drug, but on or before the last dose of study drug. Therapies in the follow-up are the therapies that were started after the last dose of study drug.

[REDACTED]

[REDACTED]

[REDACTED]

[REDACTED]

[REDACTED]

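### New anticancer therapy censors PFS and TTP, but no matching rule exists for duration of response, duration of stable disease or best response, so a few subjects can be counted inconsistently

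*SAP*

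**What the plan says.** **PFS and TTP.** SAP Table 8 has a row for "New anticancer treatment started with no claim of progression", with censoring at the last visit with an adequate assessment. SAP 10.5.2 carries this over: "The censoring rules for TTP are the same as described for PFS, except deaths without progression are censored".

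**DoR and duration of SD.** Under SAP Table 7 both run "until the first date when PD is documented or death occurred". The censoring column holds two rules only. One is "If the subject is still alive and did not experience PD at the date of cutoff, DoR and duration of SD will be censored", using the last adequate assessment before cutoff. The other applies to anyone who "progresses or dies after an extended lost-to-follow up time (two or more missed assessments), DoR and duration of SD will be censored", again at the last adequate assessment.

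**Best response.** In SAP 10.2, "BOR is derived from post-baseline responses up until the date of progression or data cut-off date" if there is no earlier progression. The irRECIST best response is taken over all post-baseline time points. Time to best response in SAP 10.4 uses any valid post-baseline assessment. Sustained disease control (SAP Table 6) needs CR, PR, or SD lasting at least 16 weeks, so it inherits the duration-of-SD rule.

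**Conduct.** Scheduled tumor assessments end at progression or new anticancer therapy (SAP 10 and Table 14; Protocol 6.4.2, 6.5 and Table 3). Scans may also be done whenever clinically indicated. Survival data continue: "After the EOT visit, all subjects will be followed for survival status", up to two years from enrollment. The SAP also classifies cancer therapies by start date: "Concomitant therapies are the therapies that were started on or after the first dose of study drug" and no later than the last dose.

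SAP section 15, which lists changes from the protocol, gives no reason for treating the endpoints differently.

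**The concern.** PFS, TTP, DoR, duration of SD and best response are built from the same scans in the same subjects, yet new therapy is recognized as a stopping point for only two of them. A subject censored for PFS under the new-therapy row could still have an open response or SD interval. That interval could then be closed by a death, or altered by a scan, that reflects another treatment. New anticancer therapy is defined in Protocol 6.4.3 to include locoregional treatment, surgery and radiation, which can act directly on measured lesions.

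Disease control rate (DCR) and DoR are secondary endpoints in the dose escalation phase (SAP Table 2), the only phase that remains after the decision recorded in SAP section 15. There is no control arm in which the same effect would cancel, and the cohorts are small enough for one subject to matter.

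**Working it through.** **1. The plan's own figures.** The plan states no figure on this point. The ORR design figures reproduce (1 − 0.80^14 = 0.956; 95% Wilson interval for 35% of 30 = 0.205 to 0.529), and no censoring rule enters them.

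**2. Side by side.**

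| Endpoint | Place in SAP | Stops at new therapy? |
|---|---|---|
| PFS | Table 8 | Yes, last adequate assessment |
| TTP | 10.5.2 | Yes, by reference |
| DoR, duration of SD | Table 7 | No rule |
| Best response, RECIST 1.1 | 10.2 | No rule |
| Best response, irRECIST | 10.2 | No rule |
| Time to best response | 10.4 | No rule |
| Sustained DCR | Table 6 | No rule (inherits duration of SD) |

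**3. Where the tables agree.** Take a subject with SD or PR at the last scan who starts new therapy, has no further scans and is alive without progression at cutoff. Table 7 censors at the last adequate assessment. Under the scan-stop rule that scan precedes the new therapy, so the date equals the one given by Table 8. Nothing is credited.

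**4. Divergence (a): death on the new therapy.** Scans fall at weeks 8, 16 and 24. Suppose SD at week 8, new therapy at week 9 and death at week 20.
- Missed assessments before death: week 16 only, so 1, fewer than 2. The missed-assessment rule does not apply.
- Table 7: duration of SD = 20 − 0 = 20 weeks, at least 16, so sustained DCR is met.
- A new-therapy rule like the one in Table 8: censored at week 8, less than 16, so sustained DCR is not shown.

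The interval from last scan to a death that still counts can reach about 2 × 8 = 16 weeks on the 8-week schedule and 2 × 12 = 24 weeks on the 12-week schedule, plus visit windows. This assumes that scans no longer scheduled after new therapy count as missed, which the SAP does not say. If they do not, a death at any later time in the two-year follow-up would close the interval.

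**5. Divergence (b): a scan after new therapy.** A clinically indicated scan, or the tumor evaluation listed for the end-of-treatment visit (Protocol 6.3), would enter best response, irRECIST best response, DoR or time to best response if it fell after new therapy began.

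**6. Size on the rates.** One subject is 1/20 = 5 points of the roughly 20 planned, or 1/6 = 16.7 points in a cohort of six. For example, 3/20 = 15% (Clopper-Pearson 3.2% to 37.9%) becomes 4/20 = 20% (5.7% to 43.7%). The direction is fixed: a longer window cannot lower the best response, and a Table 7 duration cannot be shorter than one cut at the last scan before new therapy.

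**7. Size on DoR (hypothetical).** Five responders have DoR of 8, 16, 24, 32+ and 40 weeks (+ = censored). A sixth responds at week 8, is last scanned before new therapy at week 16, and starts it at week 18.
- Censored at that scan (16 − 8 = 8+): S(24) = 5/6 × 3/4 × 2/3 = 0.417; median 24.
- Death at week 27, one scan missed, event at 27 − 8 = 19: S(24) = 5/6 × 4/5 × 3/4 × 2/3 = 0.333; median 19.
- Off-schedule scans with progression at week 64, event at 64 − 8 = 56: S(24) = 5/6 × 4/5 × 3/4 = 0.500; median 24.

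The median here is the first time the estimate is at or below 0.5. The estimate equals 0.5 exactly in the last two cases, so software that averages adjacent times would give (19 + 24)/2 = 21.5 and (24 + 40)/2 = 32. Either way, DoR can fall or rise.

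**The case against.** The strongest reply is that trial conduct already closes most of the gap. Scheduled scans end at new therapy, a subject alive without progression is then censored at the same date under either table, and the note to SAP Table 5 excludes RECIST responses after first progression. The two-missed-assessments rule also limits how long a death can extend an interval. All of this stands, except that the last limit depends on the undefined meaning of a missed scan. It does not remove divergences (a) and (b).

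A reader might infer several stronger things that the documents do not support:
- *That time and responses on another therapy are credited as a matter of course.* A response needs a scan beyond the stop point, and added time needs a death within the window above or such a scan.
- *That any such subject inflates a rate.* With PR at week 8, local therapy at week 9 and progression on a week 15 scan, no rate changes. DoR becomes a 15 − 8 = 7-week event instead of being censored at time zero. In divergence (a), ordinary DCR is also unchanged, because SD at week 8 already exceeds the 6-week minimum.
- *That Table 8 gives a clean contrast.* It censors at the last adequate assessment, not at therapy start, and does not require that assessment to precede the therapy. It also has a row making death after one missed visit an event, with no stated precedence. On that row the subject in step 4 is a PFS event at week 20, in agreement with Table 7.
- *That SAP 8.4 shows anticancer therapy during study treatment is expected.* It only sorts therapies by date. The protocol's concomitant-therapy rules are not in the available text.

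Counting outcomes regardless of later therapy would be a legitimate choice, but the SAP does not make it, and it would conflict with the Table 8 row and the scan-stop rule.

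**Conclusion.** The omission is real, unexplained and worth correcting. Its reach is narrow: deaths on new therapy before two assessments are missed, and scans taken after new therapy starts. Within that reach ORR, DCR and sustained DCR can only stay the same or rise, by 5 points per subject among 20 or 17 in a cohort of six. DoR can move in either direction.

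Materiality is limited. Analyses are descriptive, the expansion phase and futility analysis have been dropped, and no sample size depends on the rule. Divergence (a) bears on DoR and on sustained DCR and duration of SD; the last two do not appear in the visible rows of the endpoint table.

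Assumptions: 20 subjects is the planned approximate maximum; the subject histories are illustrative; the documents give no frequency for either situation; and a censored SD duration below 16 weeks is taken as not meeting sustained DCR, which the SAP leaves unstated.

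**What to change.** 1. **Table 7:** use only tumor assessments on or before the start of new anticancer therapy. If that therapy starts before progression or death, censor DoR and duration of SD at the last such adequate assessment.
2. **SAP 10.2 (RECIST 1.1 and irRECIST best response) and 10.4:** apply the same limit on which assessments are used.
3. **Sustained DCR:** require the 16 weeks of SD to be shown before any new anticancer therapy, and state how a censored SD duration is classed against that limit.
4. **Table 8:** add the same limit, and state that the new-therapy row takes precedence over the death rows.

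The cost is a few sentences. New therapies are already collected and sorted by start date, and no design figure changes. The downside is a few more censored durations and possibly a slightly lower sustained DCR.
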